2. STUDY OBJECTIVES AND MEASURES/PARAMETERS

2.1. Primary and Secondary Study Objectives and Measures/Parameters

Objectives	Measures/Parameters

The primary objective of this study is to evaluate and compare the pharmacokinetic profile of medroxyprogesterone acetate (MPA) following subcutaneous administration of 3 doses of TV-46046 300 mg/mL (120 mg/0.4mL; 180 mg/0.6mL; 240 mg/0.8mL), and 104 mg/0.65 mL of Depo-subQ Provera 104 in healthy female subjects.
	
The following non-exhaustive list of pharmacokinetic parameters will be evaluated to support the primary objective of the study:
 
 • C_{\max} (maximum observed serum concentration) • T_{\max} (time to C_{\max}) • Serum MPA concentrations at treatment days 91, 182, and 210 (C_{91}, C_{182}, C_{210}) • AUC_{0-182} (area under the serum drug concentration-time curve from time 0 to day 182); AUC_{0-210} (AUC from time 0 to day 210); and $AUC_{0-\infty}$ (AUC extrapolated to infinity) • Apparent terminal half-life ($t_{1/2}$)

The secondary objectives of the study are:
 
 1) to evaluate and compare the safety and local tolerability of a subcutaneous injection of 3 doses of TV-46046 300 mg/mL (120 mg/0.4mL; 180 mg/0.6mL; 240 mg/0.8mL) and 104 mg/0.65 mL of Depo-subQ Provera 104 in healthy female subjects. 2) to evaluate the acceptability of a subcutaneous injection of TV-46046 over the range of different doses. 	
The safety and local tolerability measures/parameters are:
 
 • occurrence of adverse events • use of concomitant medication • vital signs and body weight measurement • vaginal bleeding pattern • assessment of mood by Patient Health Questionnaire-9 (PHQ-9) • liver function tests • estradiol (E2) measurements throughout the study • progesterone (P) measurements at Weeks 48, 49, 50, 51, and 52 • occurrence of injection site reactions (ISRs) 
The acceptability parameters are:
 
 • subject's responses to acceptability questions

[figure not shown]
3. INVESTIGATIONAL PLAN

3.1. General Study Design

The assessments and procedures performed during each study visit are detailed in [Table 1](#) and [Section 3.4](#).

The study schematic diagram is presented in [Figure 1](#).

Figure 1: Overall Study Schematic Diagram

3.2. Subject Eligibility

Prospective waivers (exceptions) from study eligibility criteria to allow subjects to enter a study are not granted by Teva (see [Section 11.1.2](#)).

3.2.1. Subject Inclusion Criteria

Subjects may be included in the study if they meet all of the following criteria:

- a. willing and capable of giving signed informed consent
- b. female of 18 to 45 years of age (inclusive)
- c. healthy based on results of physical examination, medical history, vital signs tests, and Pap smear results
- d. has regular menstrual cycle (21 to 35 days)
- e. has a low risk of pregnancy (ie, sterilized, in exclusively same-sex partnership, abstinent, in monogamous relationship with vasectomized partner, using non-hormonal intrauterine device (IUD), or consistently using barrier methods of contraception)
- f. had a normal mammogram within the last year, if 40 years of age or older

- g. has a body mass index (BMI) of 18 to 35, inclusive
- h. has hemoglobin ≥ 10.5 g/dL
- i. is willing and able to comply with all study requirements and return to the investigational center for the follow-up procedures and assessments as specified in this protocol

3.2.2. Subject Exclusion Criteria

Subjects will be excluded from participating in this study if they meet any of the following criteria:

- a. has hypertension with:
 - o systolic BP ≥ 160 mm Hg or diastolic BP ≥ 100 mm Hg
 - o vascular disease
- b. has an abnormal Pap result that requires treatment or in the opinion of an investigator would make study participation unsafe or complicate data interpretation
- c. has multiple risk factors for cardiovascular disease (eg, smoking, obesity, hypertension, known low high density lipoprotein (HDL), high low density lipoprotein (LDL), or high triglyceride levels)
- d. has current or history of ischemic heart disease
- e. has active thrombophlebitis, current or past history of thromboembolic disorders, cerebral vascular disease or stroke
- f. has systemic lupus erythematosus
- g. has rheumatoid arthritis on immunosuppressive therapy
- h. has unexplained vaginal bleeding
- i. has diabetes
- j. has strong family history of breast cancer (defined as one or more first degree relatives with breast cancer, breast cancer occurring before menopause in three or more family members, regardless of degree of relationship, and any male family member with breast cancer)
- k. has current or history of breast cancer, or undiagnosed mass detected by breast exam
- l. has current or history of cervical cancer
- m. has cirrhosis or liver tumors
- n. has one or more baseline liver function test(s) outside the local laboratory's normal range
- o. has known osteoporosis or osteopenia
- p. has history of diagnosed clinical depression or bipolar disorder, with or without suicidal ideation, and/or history of suicide attempt, except short-lived situational depression that did not require medication and has not recurred in last five years

- q. has history of psychiatric disorder that in the opinion of the investigator would make study participation unsafe, would interfere with adherence to study requirements or complicate data interpretation
- r. used MPA-containing injectable products in the past 12 months
- s. used a combined injectable contraceptive in the past 6 months
- t. used any of the following medications within 1 month prior to enrollment:
 - o. any investigational drug
 - o. prohibited drugs per protocol
 - o. oral contraceptives, contraceptive ring or patch
 - o. levonorgestrel intrauterine system or contraceptive implant
- u. is participating in another clinical trial
- v. is pregnant
- w. desires to become pregnant in subsequent 24 months
- x. has been pregnant in last 3 months
- y. is currently lactating
- z. is using or planning to use prohibited drugs per protocol in the next 12 months
 - aa. has known sensitivity to MPA or inactive ingredients
 - bb. plans to move to another location in the next 12 months
 - cc. has any condition (social or medical), which in the opinion of the investigator would make study participation unsafe, would interfere with adherence to the clinical study requirements or complicate data interpretation

3.3. Duration of Subject Participation

Total duration of the study for each subject is expected to be approximately 19.5 months, including approximately 1.5 months of screening and up to 18 months of follow-up after study treatment initiation. All subjects will be followed for at least 52 weeks after treatment initiation. If subjects have unresolved ISR(s) at Week 52, they will be followed until ISR resolution or Week 78, whichever comes first. Therefore, the minimal duration of subject participation is 52 weeks and the maximum 78 weeks after treatment initiation.

See Section [12.4](#) for the definition of the end of the study.

3.4. Study Procedures

Study procedures and assessments with their timing are summarized in [Table 1](#). Detailed descriptions of each assessment are provided in Section [5](#) (safety assessments) and Section [6](#) (pharmacokinetic assessments).

Table 1: Study Procedures and Assessments

Procedures and assessments	Screening	Enrollment	Follow-Up	
	(6 Weeks before Randomization)	Day 0	Day 1 to Week 52 (Day 365)	
			Scheduled Follow-up (Day 7, Weeks 13, 26, and 52)	Lab visits ^a
Informed consent	X			
Medical history	X			
Inclusion and exclusion criteria	X	X		
Demographics, contraceptive and reproductive history	X			
Height	X			
Vital signs measurement	X	X	X	
Body weight	X	X	X	
Physical exam	X			
Urine pregnancy test ^b		X	X	X X
Randomization		X		
Study drug administration		X		
E2 ^c		X	X	X
P ^c		X	X	X
Serum MPA ^d		X	X	X
Injection site reactions ^e		X	X	X
Adverse event inquiry ^f		X	X	X

Procedures and assessments	Screening	Enrollment	Follow-Up	
	(6 Weeks before Randomization)	Day 0	Day 1 to Week 52 (Day 365)	Weeks 65 and 78
			Scheduled Follow-up (Day 7, Weeks 13, 26, and 52)	Lab visits ^a
Concomitant medication inquiry ^f		X	X	X
Hemoglobin	X			
Liver function testing ^g	X		X	
Mood evaluation ^h		X	X	X
Vaginal bleeding pattern ⁱ			X	
Mammogram ^j	X			
Pap smear ^k	X			
Acceptability ^l			X	

^a Subjects will return for laboratory visits at pre-defined time points: Days 0, 1, 2, 3, 5, 7, 10, 12, 14, 18, 21, and 28; Weeks 6, 8, 10, 12, 13, 15, 17, 19, 21, 23, 25, 26, 28, 30, and 32; and then every 28 days through Week 52.

^b An urine pregnancy test will be performed on Day 0; Weeks 26, 32, 36, 40, 44, 48, and 52; and at Weeks 65 and 78 if applicable, and at any other times when indicated.

^c Blood samples for P and E2 will be collected at Day 0 and at Weeks 48, 49, 50, 51, and 52. Blood samples for E2 will be collected at all visits when MPA or P is tested starting on Day 28.

^d Blood samples for MPA will be collected on Days 0, 1, 2, 3, 5, 7, 10, 12, 14, 18, 21, and 28; Weeks 6, 8, 10, 12, 13, 15, 17, 19, 21, 23, 25, 26, 28, 30, and 32; and then every 28 days through Week 52.

^e ISRs will be evaluated on Day 0 immediately (ie, as soon as possible but no later than 10 minutes upon removing the needle) and 1 hour (\pm 5 minutes) after injection; Day 7; at Weeks 13, 26, and 52 and at other visits, if indicated. Subjects who have ISR(s) at Week 52 will be followed every 3 months (at Weeks 65 and 78) until ISR resolution or Week 78, whichever is earlier. If the subject does not have any ISRs at Week 52 it will be her final visit. All subjects will be instructed to return to the clinic if any ISRs develop after their final visit.

^f During laboratory visits, information on adverse events and concomitant medications will not be solicited, but will be documented if self-reported by the subject. Adverse events and use of concomitant medications will also be evaluated during additional ISR follow up at Weeks 65 and 78.

^g Liver function testing will be done at Screening, Day 7 and at the Weeks 13, 26, and 52.

^h Mood will be evaluated on Days 0 and 28; Weeks 8, 13, 17, 21, 26, 32, 36, 40, 44, 48, and 52.

ⁱ Vaginal bleeding pattern will be assessed at Weeks 13, 26, and 52.

^j Normal mammogram results from within the last year must be presented prior to enrollment for women 40 years of age or older.

^k Pap test will be completed for women who do not have results of their previous Pap test that are within American College of Obstetricians and Gynecologists (ACOG) Pap test standard of care requirements. If additional testing is

required based on Pap results, this should be completed prior to enrollment (in accordance with [Committee on Practice Bulletins Gynecology 2016](#)).

¹ Acceptability data will be collected at Weeks 26 and 52.

E2= Estradiol; ISR=injection site reaction; Lab = laboratory; MPA = medroxyprogesterone acetate; P= Progesterone

3.4.1. Procedures for Screening

A signed and dated informed consent form (ICF) will be obtained before screening procedures commence (see Section [12.2](#)).

After informed consent is obtained, subjects will be assigned a subject identification number in consecutive order within each investigational center.

Demographic data as well as contraceptive and reproductive history will be collected and documented. Screening for eligibility will include, review of eligibility criteria and medical history, measurement of hemoglobin and liver enzymes, and physical examination that will include, at minimum: head/neck, ears, eyes, nose, throat, chest and lungs, cardiovascular, abdomen, skin, lymph nodes and breast assessments. BMI will be calculated based on the measured weight and height.

In addition, a mammogram will be performed for women 40 years of age or older if mammogram results from within the last year are not available. A Pap test will be performed if required, following American College of Obstetricians and Gynecologists Pap test guidelines ([Committee on Practice Bulletins Gynecology 2016](#)). In addition, investigational centers may perform additional screening procedures per their standard of care procedures (eg, STI testing, urine drug screening). All screening procedures and tests will be completed within 6 weeks before randomization.

3.4.2. Procedures for Enrollment (Day 0)

Enrollment visits will be scheduled to occur during the first 5 days of the menstrual cycle. On that day, a urine pregnancy test will be completed in all subjects to rule out pregnancy. In addition, an assessment of vital signs, body weight and BMI, mood, E2 and P, and MPA will be performed. Adverse events and concomitant medications will be evaluated.

All eligibility criteria will be verified prior to randomization.

Eligible subjects will be enrolled into the study and randomly assigned in a 1:1:1:1 ratio to receive one of the 4 study treatments: 120 mg/0.4 mL, 180 mg/0.6 mL or 240 mg/0.8 mL of TV-46046, or 104 mg/0.65 mL of Depo-subQ Provera 104. Each study treatment will consist of a single subcutaneous injection in the abdomen. The injection site location will be marked and photographed for reference. The injection site will be observed for ISRs immediately (ie, as soon as possible but no later than 10 minutes upon removing the needle) and 1 hour (± 5 minutes) after the injection.

3.4.3. Procedures for Follow-Up

Study follow-up will last for at least 52 weeks from treatment initiation. There will be four scheduled follow-up visits at Week 1 (Day 7), Week 13, Week 26, and Week 52, during which subjects will be evaluated for vital signs, body weight, liver enzymes, ISRs, adverse events and

use of concomitant medications. Vaginal bleeding pattern, acceptability and mood will be evaluated throughout the study at pre-defined time points (See [Table 1](#)). Urine pregnancy tests will be administered periodically starting at Week 26 through the end of the study.

In addition to the scheduled follow-up visits, subjects will return for laboratory visits to provide blood samples for MPA, P, and E2 at pre-defined time points (see [Table 1](#)).

If the subject has new or ongoing ISRs at Week 52, she will be followed every 3 months (at Weeks 65 and 78) until ISR resolution or Month 18 (Week 78), whichever is earlier. If the subject does not have any ISRs at Week 52 it will be her final visit. However, all subjects will be instructed to return to the clinic if any ISRs develop after their final visit. In that case, their status will change from completed the study to active and they will be followed per the schedule above until ISR resolution or Week 78, whichever is earlier.

Follow up visits should be scheduled using the target window periods below. However, if a subject cannot attend a visit within the target window below, the visit procedures should be conducted as soon as possible regardless of timing.

Table 2: Target Time Windows for Follow-up Visits

Target visit date	Target time window
Days 1, 2	± 1 hour
Days 3, 5, 7	± 3 hours
Days 10, 12, 14, 18	± 24 hours
Any scheduled clinic or laboratory visit past Day 21	± 48 hours

3.4.4. Unscheduled Procedures and Visits

An unscheduled procedure or visit may be performed at any time during the study at the subject's request or as deemed necessary by the investigator.

Unscheduled procedures may include the following:

- concomitant medication review
- vital signs measurements
- adverse event inquiry
- study compliance review
- urine pregnancy test

Other procedures may be performed at the discretion of the investigator and in consult with the sponsor.

4. TREATMENT OF SUBJECTS

4.1. Investigational Medicinal Products Administered During the Study

The IMPs used in this study are described in [Table 3](#).

4.1.1. Test Investigational Medicinal Product

Approximately 60 subjects will be randomized in a 1:1:1:1 ratio to receive one of the 4 study treatments: 120 mg/0.4 mL, 180 mg/0.6 mL or 240 mg/0.8 mL of TV-46046, or 104 mg/0.65 mL of Depo-subQ Provera 104, stratified by site.

4.1.2. Reference Investigational Medicinal Product

Depo-subQ Provera 104 is the reference investigational medicinal product (IMP). For this study, Depo-subQ Provera 104 will be supplied as a single-unit dose of 104 mg/0.65 mL prefilled glass syringes pre-packaged with 26 gauge 3/8" needle. Detailed composition and injection instructions are contained in the Depo-subQ Provera 104 Prescribing Information ([Depo-subQ Provera 104 US Prescribing Information 2016](#)).

4.2. Treatment of Subjects

TV-46046 will be administered by a study staff member as a single subcutaneous injection in the abdomen during the first 5 days of the menstrual cycle using a 23 gauge 3/8 inch needle following the sponsor's instructions for administering a subcutaneous injection. The clinical staff preparing the dose and providing the injections will be trained to shield the syringe from view of the subject and any blinded study staff prior to and at the time of injection.

Table 3: Investigational Medicinal Products Used in the Study

IMP name	TV-46046		Reference IMP	
Trade name and INN, if applicable, or company assigned number	Medroxyprogesterone acetate injectable suspension 300mg/mL		Depo –SubQ Provera 104® Medroxyprogesterone acetate injectable suspension (104 mg/0.65mL for sc use)	
Formulation	Medroxy-progesterone Acetate	300 mg	Medroxy-progesterone acetate	104 mg
	Docusate sodium	0.60 mg	Methylparaben	1.040 mg
	Polyethylene glycol 3350	20.00 mg	Propylparaben	0.098 mg
	Sodium sulfate anh.	13.00 mg	Sodium Chloride	5.200 mg
	Monobasic sodium phosphate anh.	0.60 mg	Polyethylene Glycol	18.688 mg
	Dibasic Sodium phosphate anh.	0.23 mg	Polysorbate 80	1.950 mg
	L-Methionine	1.50 mg	Monobasic Sodium Phosphate · H ₂ O	0.451 mg
	Water for Injection (up to 1 mL)	qs	Dibasic Sodium Phosphate · 12H ₂ O	0.382 mg
	NA	NA	Methionine	0.975 mg
	NA	NA	Povidone	3.250 mg
Unit dose strength(s)/Dosage level(s)	NA		Water for injection (up to 0.65 mL)	qs
	120 mg/0.4 mL		104 mg/0.65 mL	
	180 mg/0.6 mL			
Route of administration	240 mg/0.8 mL			
	SC injection		SC injection	

anh=anhydrous; H₂O =water; IMP= investigational medicinal product; INN= international nonproprietary name; NA=not applicable; qs=quantity sufficient; SC=subcutaneous

4.3. Blinding/Unblinding

This study will be partially-blinded due to differences in appearance and volume of the treatments. Designated unblinded study staff will conduct randomization procedures. The staff preparing and administering study injections will be unblinded but will be trained to shield the syringe prior to and at the time of injection from view of the subject and any other blinded study staff. FHI 360 and sponsor project team members involved in assessment of adverse events, data analysis or results interpretation will be blinded to treatment assignment until the planned interim analysis, after which only investigational center staff performing subject interviews and

assessing safety outcomes will remain blinded. Lab personnel performing MPA testing will remain blinded to treatment assignment throughout the study.

4.3.1. Unblinding During the Study

A description of the emergency unblinding procedures will be included in the study pharmacy manual.

For adverse events that are defined as a Suspected Unexpected Serious Adverse Reaction (SUSAR) (ie, reasonable possibility that adverse event is related to treatment; Section 5.2.5), Global Patient Safety and Pharmacovigilance will request that the treatment code be revealed to comply with regulatory requirements. The report will be provided in an unblinded manner for regulatory submission. In the case of a SUSAR, only the sponsor and a designated unblinded FHI 360 staff will receive the unblinded report for regulatory submission; other staff will receive a blinded report in accordance with sponsor's current procedures.

All cases of inadvertent unblinding will be handled per FHI 360's standard operating procedures (SOPs).

4.4. Stopping Rules and Discontinuation Criteria

If, at any time one of the following occurs: two or more ISRs graded as severe adverse events, 15 cases of skin discoloration at injection site (eg, hypopigmentation) ongoing for more than 7 days, or two serious and related adverse events in the study across all treatment groups, an unplanned review of interim data by a Study Review Committee (SRC), will occur, at which time a recommendation may be made to pause enrollment or halt the study. Other planned reviews will take place as scheduled (see Section 9.8), at which time the SRC could advise that the study stop or be modified based on concerns for safety of subjects or definitive conclusions.

Since most of the study drugs are expected to remain in the body months after injection, study discontinuation will not be the same as treatment discontinuation. Study staff will explain to subjects who wish to discontinue the study early that it is important to stay in the study until safety assessments are completed. However, a subject may discontinue participation in the study at any time for any reason (eg, withdrawal of consent or an adverse event) without loss of other benefits or services to which they may be entitled. All subjects who discontinue early will be followed according to Subject Withdrawal Criteria and Procedures (Section 4.9.1). Reasons for discontinuation from the study will be recorded on the appropriate electronic case report form (eCRF).

Others reasons the study may be stopped include:

- Institutional Review Board (IRB)/ Independent Ethics Committee (IEC) recommend terminating the study
- The Food and Drug Administration (FDA) requests that the study be discontinued or placed on hold.
- The sponsor decides to reduce the scope (eg, reduce sample size, drop one or more study groups) or terminate the study. The sponsor may terminate the study at any time for any reason.

If the whole study is stopped, the subjects that are terminated early will be followed according to Subject Withdrawal Criteria and Procedures (Section [4.9.1](#)).

4.5. Interim Data Reviews

The study will be overseen by an internal SRC, the composition and responsibilities of which will be detailed in a separate SRC Operational Plan. External consultants with relevant specialties may also be engaged as part of this SRC.

The SRC will convene for at least one review of interim data after at least 80% of subjects have had a chance to complete 7.5 months after treatment initiation. This analysis is intended to help inform the decision to move to, and select the dose for, a pivotal study. In addition, unplanned reviews may be triggered by the occurrence of ISRs, injection site discoloration (hypopigmentation) events and/or serious and related adverse events. At the time of any planned or unplanned interim review of data, the SRC may recommend that the trial be modified or halted to ensure the safety and well-being of study subjects. There will be no adjustment to type I error to account for any interim reviews of study data.

4.6. Prior and Concomitant Therapy or Medication

Any prior or concomitant medication a subject has had within 30 days before study drug administration and up to the final visit will be recorded as a concomitant medication on the appropriate CRF. During the four scheduled follow-up visits the investigator will ask subjects whether they have taken any medications, including over-the-counter medications, vitamins, or herbal or nutritional supplements, since the previous visit. During all other visits information on the use of concomitant medications will be documented only if self-reported by the subject. Generic or trade name, indication, route of administration, dosage, and start and end dates will be recorded.

The following medications should not be used during this study: aminoglutethimide; steroid hormones (estrogens, progestins and androgens); and antiretroviral drugs including non-nucleoside reverse transcriptase inhibitors (efavirenz and nevirapine) and ritonavir-boosted protease inhibitors. The use of prohibited drugs will be documented as an important protocol deviation. In addition, application of bandages to injection sites will be discouraged.

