9.9. Planned Interim Analysis

At least one interim review is planned to occur after at least 80% of subjects have had a chance to complete 7.5 months after treatment initiation. This analysis is intended to help inform the decision to move to, and select the dose for, a pivotal study. These interim data may be used to inform the end of Phase 1 meeting with the FDA.

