2.3. Blinded Data Review

Prior to the first planned interim analysis, study data will be reviewed by the Coordinating Investigator and Lead Biostatistician or their designee(s) to inform analysis decisions. The Lead Biostatistician will be responsible for developing blinded listings for this review and will document the Coordinating Investigator's decisions prior to unblinding. These reviews will include (but not necessarily be limited to) important protocol deviations for inclusion/exclusion of subjects and/or data points from the primary analysis sets, assessment of potential outliers, and any necessary adjustments to imputation rules for missing MPA results due to out of window visits. Blinded data reviews may likewise occur to inform clinical queries to the site.

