10.3. Intercurrent Events

A single IcE is anticipated as possibly occurring in this study: the use of concomitant medications known to impact the pharmacokinetics of MPA. Any MPA results obtained from a subject between the initiation date of a relevant medication and the last date that the medication may have impacted the pharmacokinetics of MPA will be excluded from the Pharmacokinetics Analysis Set. This strategy corresponds to the hypothetical scenario in which the IcE did not occur when defining pharmacokinetic estimands, and the corresponding estimators will be (asymptotically) unbiased under the assumption that the excluded data are missing completely at random (i.e., the reason for use of the medication is independent of the pharmacokinetics of MPA). The precise dates of exclusion will be adjudicated by the Lead Biostatistician and Clinical Investigator in blind review whenever possible. The impact of exclusions on pharmacokinetic parameter estimators are described further in Section 10.4.

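### Medication use is not asked about between Week 26 and Week 52, so the SAP's exclusion rule cannot be applied reliably to C210 at the dose-selection interim

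*Protocol*

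**What the plan says.** **Ascertainment.** Protocol 4.6 states: "During the four scheduled follow-up visits the investigator will ask subjects whether they have taken any medications". Protocol 3.4.3 dates these visits: "There will be four scheduled follow-up visits at Week 1 (Day 7), Week 13, Week 26, and Week 52". For the rest, 4.6 says "During all other visits information on the use of concomitant medications will be documented only if self-reported by the subject", 5.1.2 says the same, and Table 1 footnote f repeats it: "During laboratory visits, information on adverse events and concomitant medications will not be solicited, but will be documented if self-reported by the subject". Medication use is also evaluated at Day 0 and, for women still followed for injection site reactions, at Weeks 65 and 78. Start and end dates are recorded for each drug.

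**Use in the analysis.** SAP 10.3 specifies which data leave the Pharmacokinetic Analysis Set: "Any MPA results obtained from a subject between the initiation date of a relevant medication and the last date" on which the drug may have had an effect. The exclusion dates are to be adjudicated in blind review where that can be done. SAP 3.4 gives CYP3A4 inducers and inhibitors as examples of relevant drugs. That is wider than the prohibited list in Protocol 4.6, so a permitted drug can trigger the rule.

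**Timing.** Protocol 9.9 places the interim "after at least 80% of subjects have had a chance to complete 7.5 months after treatment initiation" and says it is to help choose the pivotal-study dose. SAP 2.3 puts the blinded review of exclusions before it: "Prior to the first planned interim analysis, study data will be reviewed by the Coordinating Investigator and Lead Biostatistician". Under Protocol 4.3 the sponsor and implementing team lose their blind at the interim.

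**The concern.** The rule in SAP 10.3 can act only on drugs that someone has recorded. From Week 26 to Week 52 women attend for MPA draws at Weeks 28, 30, 32, 36, 40, 44 and 48, and at none of these are they asked about medication. C210, a primary parameter, is the Week 30 draw. The interim can take place after C210 has been measured but before the next question is put.

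Two things are at stake. At the interim, a concentration altered by an inhibitor or inducer may stay in the primary set unrecognised. At the final analysis, use first reported at Week 52 has to be adjudicated by a team that already knows the treatment assignments.

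**Working it through.** **1. Sampling schedule (Table 1 footnote d; SAP 2.1).** Day 0 to Day 28 gives 12 draws, Weeks 6 to 32 give 15, and Weeks 36 to 52 give 5. 12 + 15 + 5 = 32, which matches the 32 MPA samples in Protocol Table 4. Of these, 31 are post-dose.

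**2. Draws by interval between solicited questions.**

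| Interval ending at the question | Length (days) | MPA draws |
|---|---|---|
| Day 0 to Day 7 | 7 | 5 |
| Day 7 to Week 13 (Day 91) | 84 | 11 |
| Week 13 to Week 26 (Day 182) | 91 | 7 |
| Week 26 to Week 52 (Day 364) | 182 | 8 |

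Read as looking back to the previous solicited question, the Week 26 inquiry completes coverage of 5 + 11 + 7 = 23 of the 31 post-dose draws before the interim.

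**3. Position of the interim.** 7.5 months × (365.25/12) = about Day 228. The last question was at Day 182. The draws since then are Weeks 28, 30 and 32 (Days 196, 210 and 224). Two of these fall on or before Day 210. C210 lies 210 − 182 = 28 days after the last question and 364 − 210 = 154 days (22 weeks) before the next. Use during Days 182 to 210 would be recalled 22 to 26 weeks later.

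**4. Share of women affected at the interim (accrual assumed).** The planned 26 months less 19.5 months per woman leaves about A = 6.5 months of accrual, taken as uniform. The earliest interim is at 0.8A + 7.5 = 12.7 months. Week 52 is 11.96 months and Day 210 is 6.90 months.
- Reached Week 52: (12.7 − 11.96)/6.5 = 11.4% of all women.
- Reached Day 210: (12.7 − 6.90)/6.5 = 89.2%.
- Of those with Day 210 data, without a Week 52 question: 1 − 11.4/89.2 = about 87%.

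The same calculation gives 100% for 3 months of accrual, 59% for 10 and 46% for 13.

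**5. Size for C210 (effect assumed).** If k of 15 women have C210 multiplied by f, the arm geometric mean changes by f^(k/15).
- One woman doubled: 2^(1/15) = 1.047, or +4.7%. One halved: 0.955, or −4.5%.
- Two women doubled: 2^(2/15) = 1.097, or +9.7%. Two halved: 0.912, or −8.8%.

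**6. Size for AUC0-210.** Only Days 182 to 210 are exposed, 28/210 = 13.3% of the time. With mono-exponential decline the share of area is s = (e^(−182λ) − e^(−210λ))/(1 − e^(−210λ)). For the half-lives in Protocol 1.2.2.1, 42.34 and 82.87 days, s = 1.9% and 5.5%; a flat profile gives 13.3%. One woman halved over that stretch moves the arm geometric mean by (1 − s/2)^(1/15) = 0.9994, 0.9981 or 0.9954, at most about −0.5%.

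**7. Trough comparison.** SAP 10.6 compares C182 (test) with C91 (reference). Days 182 and 91 are both days on which the question is asked.

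**8. Terminal slope.** SAP 10.5 fits λ to the last three or more quantifiable points after Cmax, the number being chosen by adjusted R². For a woman at Day 228 a three-point fit would use only the Week 28, 30 and 32 draws. The number of points varies by woman, so I give no size for t1/2 or AUC0-∞.

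**The case against.** The strongest reply is that the scheme is deliberate and stated consistently, and that the exposure is narrow. The question looks back with start and end dates, so one might wrongly count as uncovered every draw taken on a day without a question; draws through Week 26 are in fact covered by Day 182. Participants are healthy, and those using or planning prohibited drugs are excluded. Unscheduled medication review is allowed (Protocol 3.4.4), and blinded review may prompt site queries (SAP 2.3). The shift is also small beside sampling error. With an assumed geometric CV of 30% to 60%, σ = √ln(1 + CV²) and 90% limits exp(±1.701·σ·√(2/15)), the interval for a geometric mean ratio runs from −17%/+20% to −29%/+41%.

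Most of this stands, and it limits the point to C210 and late-slope quantities. It does not remove it. Unscheduled review and queries are optional and need a prompt. The Safety Set repeat in SAP 10.7 restores excluded data, so it shows whether late exclusions matter but cannot find unreported use. Wide intervals do not correct a bias.

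Three stronger readings are tempting and are not supported:
- That AUC0-210 is impaired as much as C210: step 6 shows otherwise.
- That the rule has no content at the final analysis: Week 52 still asks every woman remaining in follow-up.
- That adjudication after unblinding breaches the SAP: SAP 10.3 asks for blind review only where possible, so later adjudication is foreseen.

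**Conclusion.** The point holds for the samples after Week 26, above all C210 at the interim. A woman at 7.5 months has no solicited medication record after Day 182, so the SAP 10.3 rule cannot be applied reliably to her Week 28, 30 and 32 draws. At the final analysis the rule is weak rather than empty. It rests on recall of about 22 to 26 weeks for the first draws in the gap, and use first reported then is adjudicated after the team is unblinded.

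One wording problem adds to this. Protocol 4.6 asks about use since the previous visit without defining that visit. Taken literally at Week 52, it would mean the Week 51 progesterone visit, and Days 182 to 210 would never be asked about. The coverage through Week 26 in step 2 depends on the more generous reading.

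The size rests on assumptions, because the documents give neither the frequency of interacting drugs nor the size of their effect. One unrecognised two-fold change in 15 gives about 4.7% on the C210 geometric mean; for AUC0-210, one woman halved after Day 182 gives about 0.5% or less. This is a cheap improvement to a primary parameter available at dose selection. It is not a defect that invalidates the plan.

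**What to change.** Amend Protocol 4.6, 5.1.2 and Table 1 footnote f so that the standard non-leading medication question is also asked at Week 32, with start and stop dates. Define its look-back as the time since the last solicited inquiry, and use that definition at Week 52 too. Week 32 is Day 224 (Days 222 to 226 with the ±48-hour target window). It therefore follows C210 and precedes Day 228, and C210 exclusions can be adjudicated blind before the interim. Preferably add the question at Weeks 36, 40, 44 and 48 as well, which would shorten recall for the later draws. Mood is already evaluated at all five of these visits. SAP 10.3 should state the ascertainment limit for any woman without a solicited record after Week 26.

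The cost is a short amendment, one question at visits that already take place, and a few more medication records to enter and code. No visit or blood sample is added.
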